## 1. LIST OF ABBREVIATIONS

Abbreviation	Definition
1L	First-line
2L	Second-line
AE	Adverse event
CCI	
CIOMS	Council for International Organizations of Medical Sciences
EMA	European Medicines Agency
ENCePP	European Network of Centres for Pharmacoepidemiology and Pharmacovigilance
GEP	Good Epidemiological Practice
GPP	Guidelines for Good Pharmacoepidemiology Practices
Hb	Hemoglobin
IEA	International Epidemiological Association
IEC	Independent Ethics Committee
IMDC	International Metastatic Renal Cell Carcinoma Database Consortium
IO	Immuno-oncology
IQR	Interquartile range
IRB	Institutional Review Board
ISPE	International Society for Pharmacoepidemiology
ISPOR	International Society for Pharmacoeconomics and Outcomes Research
KPS	Karnofsky performance status
LLN	Lower limit of normal
LSLV	Last subject last visit
mRCC	Metastatic renal cell carcinoma
mTOR	Mammalian target of rapamycin
ORR	Objective response rate
OS	Overall survival
PD-1	Programmed cell death protein 1
PD-L1	Programmed death-ligand 1
PFS	Progression-free survival
RCC	Renal cell carcinoma
SD	Standard deviation
TKI	Tyrosine kinase inhibitors
TTD	Time to treatment discontinuation
ULN	Upper limit of normal
US	United States
VEGFR	Vascular endothelial growth factor receptor

### **3. AMENDMENTS AND UPDATES**

None.

#### 4. MILESTONES

Milestone	Planned date
Start of data collection	October 2019
End of data collection For studies with primary data collection, enter the planned date for last subject last visit (LSLV). For studies with secondary data collection, enter the planned date on which the analytical dataset will be first completely available; the analytic dataset is the minimum set of data required to perform the statistical analysis for the primary objective(s).	November 2019
Final study report Enter the planned date for approval of final study report. For NI PASS protocols, the final study report must be submitted within 12 months of the end of data collection.	January 2020

#### 5. RATIONALE AND BACKGROUND

An estimated 400,000 new cases of kidney cancer, of which renal cell carcinoma (RCC) accounts for approximately 90%, are diagnosed worldwide every year. RCC comprises 2-3% of all adult malignancies, with approximately 63,000 incident cases and 14,000 deaths from RCC each year in the United States (US). Due to the lack of early symptoms and clinical indications of disease, around 20% of patients present with the most advanced stage of the cancer, metastatic RCC (mRCC), at time of diagnosis. Prognosis is poor among mRCC patients, with 5-year survival rates of 5-10%. The burden of mRCC is projected to grow with the aging population and increasing prevalence of risk factors for RCC, such as obesity and hypertension.

During the last decade, targeted therapies, which are agents that target the vascular endothelial growth factor (VEGF), VEGF receptor (VEGFR), or the mammalian target of rapamycin (mTOR), became standard of care for patients with mRCC. Since 2005, several targeted therapies have been approved for the treatment of mRCC in the US, including bevacizumab (Avastin®), sunitinib (Sutent®), sorafenib (Nexavar®), pazopanib (Votrient®), axitinib (Inlyta®), cabozantinib (Cabometyx®, Cometriq®), everolimus (Afinitor®), and temsirolimus (Torisel®). Targeted therapies have been associated with improved progression-free survival (PFS) and overall survival (OS), favorable side effect profiles, and improved health-related quality of life.

Yet, recent advancements in immuno-oncology (IO) therapeutic agents have changed the treatment paradigm for mRCC. IO therapies work by blocking immune checkpoints (eg, programmed death-1 [PD-1]/PD-ligand 1 [PD-L1]) and restoring tumor-specific T-cell-mediated immune responses, and have demonstrated antitumor activity and durable responses in both pre-treated and treatment naïve mRCC. Specifically, among mRCC patients with intermediate or poor prognostic risk, the IO combination therapy of nivolumab (Opdivo®) plus ipilimumab (Yervoy®) showed higher OS and objective response rate than sunitinib. Two recent phase 3 trials reported that patients treated with 1L IO therapies in combination with VEGFR-tyrosine kinase inhibitors (TKI) also had improved PFS and/or OS outcomes compared to patients treated with 1L sunitinib. However, despite promising early results of 1L IO therapy, some patients develop progressive disease requiring subsequent systemic therapy.

Clinical decisions on optimal treatment sequences for patients with mRCC who discontinue IO therapy have been challenging for practitioners, since treatment guidelines and regulatory policies are not yet available. Further, real-world evidence on the effectiveness of treatment sequences for patients with mRCC who discontinue IO therapy is limited. Several studies have suggested antitumor activity of targeted therapy after PD-1/PD-L1 inhibition. One retrospective study examined targeted therapies following IO therapy and found that both VEGFR-TKI and mTOR inhibitor demonstrated antitumor activity following PD-1/PD-L1 blockade. A recent retrospective study showed that among clear cell mRCC patients treated with second-line (2L) VEGFR-TKI after 1L IO therapy, 2L antitumor activity and tolerance was comparable to that in 1L TKI based on historical data. Another retrospective analysis found that clinical activity of subsequent VEGFR-TKI therapy after IO therapy was affected by the 1L combination therapy. That is, among mRCC patients treated with 2L VEGFR-TKI, patients treated with IO only in 1L showed numerically higher ORR compared to patients treated with IO in combination with anti-VEGFR. However, these studies have only included mRCC patients enrolled in clinical trials, and thus lack generalizability to real-world clinical settings.

Given this gap in the literature, we will use real-world clinical data from the International Metastatic RCC Database Consortium (IMDC) database to evaluate clinical outcomes among patients with mRCC treated with IO therapies in 1L followed by sunitinib in 2L.

## **6. RESEARCH QUESTION AND OBJECTIVES**

The study aims to assess the clinical effectiveness of 2L sunitinib following IO therapy in 1L (ie, IO monotherapy, IO + VEGFR, or nivolumab + ipilimumab), among patients with mRCC. The specific objectives are as follows:

- To describe patient demographic and clinical characteristics among patients with mRCC treated with IO in 1L followed by sunitinib in 2L.

- To characterize the following clinical outcomes in patients with mRCC treated with IO in 1L followed by sunitinib in 2L, overall and stratified by IMDC prognostic risk groups, pending on sample size:
  - OS;
  - Time to treatment discontinuation (TTD);
  - Reasons for treatment discontinuation;
  - Physician-assessed best response.
- To describe treatment patterns among patients with mRCC treated with IO in 1L followed by sunitinib in 2L (eg, duration of IO therapy, duration of sunitinib therapy, time from IO therapy discontinuation to initiation of sunitinib therapy).

[figure not shown]
## 7. RESEARCH METHODS

### 7.1. Study Design

This is a retrospective, longitudinal cohort study that involves the analysis of retrospective data collected through the IMDC database for selected academic clinical sites participating in this study (detail on clinical sites is provided in [Section 7.4](#)). A cohort of patients treated with sunitinib as the 2L therapy after treatment with IO agents as 1L therapy will be assessed.

The *index date* will be defined as the date of initiation of 2L sunitinib therapy. The *baseline period* will be defined as the time from mRCC diagnosis to the index date. The *follow-up period* will be defined as the time from the index date to the earliest of death or end of data availability. Figure 1 depicts the study design scheme.

**Figure 1. Study Design Scheme**

## 7.2. Setting

### 7.2.1. Inclusion Criteria

Patients will be selected based on the eligibility criteria listed below. Participation in an interventional trial for mRCC disease is allowed. Subjects will be selected irrespective of their survival status.

Patients must meet all of the following inclusion criteria to be eligible for inclusion in the study:

- Diagnosed with mRCC;
- Received IO therapy as 1L therapy;
- Received sunitinib as 2L therapy;
- Age 18 years or over at the time of mRCC diagnosis;
- Actively treated at an IMDC clinical center (to avoid incomplete data).

### 7.2.2. Exclusion Criteria

There are no exclusion criteria for this study.

## 7.3. Variables

### Primary exposure

- Sunitinib as 2L therapy following IO as 1L therapy.

### Outcomes

- OS, defined as the time between initiation of 2L sunitinib therapy and death.
- TTD, defined as the time between initiation of 2L sunitinib therapy and discontinuation of therapy for any reason including progression, death, and toxicity.
  - TTD for 1L IO (ie, time between initiation of 1L IO and discontinuation of therapy for any reason).
- Time to initiation of 2L sunitinib from discontinuation of 1L IO.
- Reasons for treatment discontinuation in 1L IO and 2L due to:
  - Disease progression;
  - Toxicity;

- Death;
- Other reasons.
- Physician-assessed best response in 2L while being treated with sunitinib, defined as the objective response rate (ORR) (sum of partial response and complete response), progressive disease, and stable disease.

Covariates (assessed during the baseline period or on index date)

- Gender;
- Age at time of 2L sunitinib initiation;
- Race **CCI**;
- Date of mRCC diagnosis;
- Prior nephrectomy status;
- **CCI**.
- Histology type:
  - Non-clear cell RCC;
  - Clear cell RCC.
- Number of metastatic sites (eg, 1 site or more than 1 site).
- Site of metastases (eg, brain metastasis, bone metastasis).
- IMDC prognostic risk factors:
  - Time from RCC diagnosis to systemic treatment initiation <1 year.
  - Karnofsky performance status (KPS) <80%.
  - Hemoglobin <lower limit of normal (LLN).
  - Serum corrected calcium >upper limit of normal (ULN).
  - Neutrophil count >ULN.
  - Platelet count >ULN.

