#### 7.4. Data Sources

Data will be obtained retrospectively from the IMDC clinical sites.

The IMDC cohort is a multi-institutional cohort that collects data globally from international cancer centers in the United States, Canada, Denmark, Greece, South Korea, Australia, New Zealand, Japan, Singapore, Italy, and Belgium. Demographic, clinical, laboratory, and outcome data on patients with mRCC are collected retrospectively from medical charts using uniform database templates and standardized definitions to ensure data are collected consistently. Medical records include longitudinal information on patient demographic and disease characteristics, oncology-specific workups and evaluations, treatment types and duration, concurrent diagnoses as documented in physician notes, and treatment discontinuation/halt decisions.

CCI [REDACTED] will collaborate with [name] [REDACTED] from the University of Calgary. PPD [REDACTED] who will serve as the principal investigator for this study and who is also the Chair of the IMDC, to obtain data from clinical centers. The clinical centers send data to the IMDC database, and data cleaning and consolidation of the data occur twice a year.

For this proposed study, a "limited" dataset of patients treated with 1L IO therapy and 2L sunitinib therapy will be provided only. The "limited" dataset will be anonymized and will not contain any personal data. All 1L IO and 2L sunitinib patients are included in the "limited" dataset, but only a select number of variables necessary to fulfill the study objectives will be included.

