#### 7.5. Study Size

The IMDC database has 73 patients who received 1L IO and 2L sunitinib. Power calculations were not performed as the objectives were descriptive.

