### **Description of demographic and clinical characteristics among patients with mRCC treated with 2L sunitinib therapy following 1L IO therapy**

Baseline demographic and clinical characteristics prior to or on the index date will be described using the mean (standard deviation [SD]) and median (interquartile range [IQR]) values for continuous variables and frequency distributions for categorical variables.

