### **Characterization of clinical outcomes among patients with mRCC treated with 2L sunitinib therapy following 1L IO therapy**

The clinical outcomes will be analyzed as follows:

- OS and TTD will be analyzed using Kaplan-Meier estimator;
- Reasons for 1L IO and 2L sunitinib therapy discontinuation will be described using relative frequencies;
- Physician-assessed best tumor response (ie, ORR, stable disease, and progressive disease) to 2L sunitinib therapy will be described using relative frequencies.

Stratification by IMDC prognostic risk groups (ie, favorable, intermediate, and poor) may be performed pending on sample size. One interim analysis will be performed to examine sufficiency of sample size and duration of follow-up.

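### Does the wide baseline window let pre-first-line values of KPS and laboratory tests define the IMDC risk group at sunitinib start?

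*Combined protocol and SAP*

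**What the plan says.** Section 7.1 sets the index date: it "will be defined as the date of initiation of 2L sunitinib therapy". On the stretch of time leading up to that date, which it calls baseline, the same section states that it "will be defined as the time from mRCC diagnosis to the index date".

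Section 7.3 opens the covariate list with "Covariates (assessed during the baseline period or on index date". The list contains six IMDC factors. Five are measurements with a cut-off but no stated visit: KPS, hemoglobin, corrected calcium, neutrophils and platelets. The sixth is an interval between diagnosis and systemic treatment, which needs no measurement visit. One covariate in the same list is tied to a date: "Age at time of 2L sunitinib initiation".

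Section 7.7 repeats the window: "Baseline demographic and clinical characteristics prior to or on the index date will be described". On use of the risk groups it says: "Stratification by IMDC prognostic risk groups (ie, favorable, intermediate, and poor) may be performed pending on sample size". Section 6 attaches the same condition to the stratified display of OS, TTD, reasons for discontinuation and best response.

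Section 7.4 says the source database uses common templates and definitions, and that in the extract "only a select number of variables necessary to fulfill the study objectives will be included". Section 7.5 gives the size: "The IMDC database has 73 patients who received 1L IO and 2L sunitinib". It adds that no power calculation was made because the aims are descriptive.

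**The concern.** Performance status and blood values can change during a full line of immunotherapy. A value taken before that line and one taken on the day sunitinib starts both fall inside the stated window. Two analysts could follow the text and put the same patient in different risk groups. That age is tied to sunitinib start, while these five factors are not, makes the omission more noticeable.

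Two outputs are at stake. The risk rows of the baseline table might describe patients as they were before first-line treatment, although the cohort is indexed at second line. If the optional stratification is done, outcomes counted from sunitinib start could be grouped by outdated risk. Patients who had worsened would then sit in groups that look healthier than they are, which would pull down the survival shown for those groups and understate the share at poor risk. The extract carries only selected variables, so a missing assessment date might not be recoverable later.

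**Working it through.** **Step 1: what the text permits.** Sections 7.1, 7.3 and 7.7 agree with one another. Together they set a window from mRCC diagnosis to sunitinib start. What is missing is a rule for choosing among several values within it. A pre-first-line value is allowed; it is not required. Section 7.4 mentions standard definitions but gives no timing, so it does not close the gap. It also does not say whether the extract holds one value per patient, one per treatment line, or several.

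**Step 2: which outputs depend on the choice.**

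| Output | Depends on which value is used? |
|---|---|
| Overall OS, TTD, best response, discontinuation reasons | No |
| Treatment patterns (durations and gaps) | No |
| IMDC rows of the baseline table | Yes |
| Results by risk group | Yes, if the optional stratification is done |

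The plan specifies no covariate adjustment and no test between risk groups.

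**Step 3: possible size.** The plan has no figure to reproduce. Only the 73 comes from the documents; every other input here is assumed.

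- Risk mix before first line: 20% favourable, 60% intermediate, 20% poor.
- Median OS from sunitinib start by true group at that time: 30, 16 and 6 months, exponential.
- A fraction *w* = 0.2 to 0.4 of favourable and intermediate patients worsens by one group; none improves.
- A fraction *q* of patients is labelled from pre-first-line values, the rest from values at sunitinib start.

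Share misclassified = *q* × 0.80 × *w*, because 80% start in a group that can worsen. At *q* = 0.5 this is 0.5 × 0.80 × 0.2 = 8% to 0.5 × 0.80 × 0.4 = 16%, or 73 × 0.08 = 5.8 to 73 × 0.16 = 11.7 patients.

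The true poor share is 0.20 + 0.60 × *w* = 32% to 44%. The share shown is *q* × 0.20 + (1 − *q*) × the true share.

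Each labelled group is a mixture, and its median *t* solves Σ weight × 0.5^(*t*/group median) = 0.5. For example, with *q* = 1 and *w* = 0.2 the intermediate label holds 80% intermediate and 20% poor patients. Then 0.8 × 0.5^(13.0/16) + 0.2 × 0.5^(13.0/6) ≈ 0.456 + 0.045 ≈ 0.50, so *t* = 13.0 months.

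| *q* | Misclassified | Of 73 | Favourable median (true 30) | Intermediate median (true 16) | Poor median (true 6) | Poor share shown (true 32–44%) |
|---|---|---|---|---|---|---|
| 0 | 0% | 0 | 30 | 16 | 6.0 | 32–44% |
| 0.25 | 4–8% | 3–6 | 28.9–27.3 | 15.1–14.1 | 6.0 | 29–38% |
| 0.5 | 8–16% | 6–12 | 27.9–25.4 | 14.3–12.6 | 6.0 | 26–32% |
| 1 | 16–32% | 12–23 | 26.3–23.0 | 13.0–10.5 | 6.0 | 20% |

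If 10% of intermediate and poor patients also improve by one group, the *q* = 0.5 case gives 0.5 × (0.80 × *w* + 0.80 × 0.1) = 12–20% misclassified and an intermediate median of 14.7–12.9 months.

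**Step 4: sampling error for comparison.** Assume 73 × 0.60 ≈ 44 intermediate patients, of whom 70% have died: 44 × 0.7 ≈ 31 deaths. An approximate 95% interval for a 16-month median is 16 × exp(±1.96/√31), about 11 to 23 months. The shifts at *q* = 0.25 and 0.5 lie inside it. Only the extreme corner (*q* = 1, *w* = 0.4, median 10.5) falls just outside.

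**The case for a change.** The strongest case for a change is that accurate description is the whole product of a descriptive study, and that describing baseline characteristics is not conditional on anything. One sentence in Section 7.3 would settle the choice before anyone sees outcomes by risk group, and asking for assessment dates before the transfer costs little. Systematic misclassification is also a different thing from imprecision, so a wide interval does not excuse it.

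Much of this stands. The text leaves the choice open, standard definitions do not supply a timing rule, and the baseline table is exposed even if no stratified curve is drawn. Number and site of metastases have the same open timing.

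What does not follow is that the plan leads to a wrong result. Harm needs three things that the documents do not show: that several values per patient exist, that an analyst picks an old one over a current one, and that risk group changes often between lines. A stricter rule has limits too. Barring only pre-first-line values would still admit one from the first week of immunotherapy. If the extract holds only first-line values, such a rule would leave all 73 patients without a risk group.

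**Conclusion.** The concern does not call for a change to the plan. A window is set; what is missing is a selection rule inside it, and analysts can be expected to fill that sensibly. The cohort is indexed at sunitinib start, age is taken there, and the outcomes run from there, so values at or nearest that date are the natural choice. If the database holds only first-line values, labelling the group as risk at first-line start in the report would describe it correctly.

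The certain exposure is a few rows of one table. Results by risk group are exposed only if the optional stratification is done, and the overall results are not exposed at all. The size cannot be derived from the documents. The illustration runs from no effect to 12–23 of 73 patients misplaced, and the upper end requires every patient to be labelled from a pre-first-line value. The conclusion rests on ordinary analytic practice in choosing the value. It would be weaker if the extract were found to mix values from different times without dates.

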#### 7.4. Data Sources

Data will be obtained retrospectively from the IMDC clinical sites.

The IMDC cohort is a multi-institutional cohort that collects data globally from international cancer centers in the United States, Canada, Denmark, Greece, South Korea, Australia, New Zealand, Japan, Singapore, Italy, and Belgium. Demographic, clinical, laboratory, and outcome data on patients with mRCC are collected retrospectively from medical charts using uniform database templates and standardized definitions to ensure data are collected consistently. Medical records include longitudinal information on patient demographic and disease characteristics, oncology-specific workups and evaluations, treatment types and duration, concurrent diagnoses as documented in physician notes, and treatment discontinuation/halt decisions.

CCI [REDACTED] will collaborate with [name] [REDACTED] from the University of Calgary. PPD [REDACTED] who will serve as the principal investigator for this study and who is also the Chair of the IMDC, to obtain data from clinical centers. The clinical centers send data to the IMDC database, and data cleaning and consolidation of the data occur twice a year.

For this proposed study, a "limited" dataset of patients treated with 1L IO therapy and 2L sunitinib therapy will be provided only. The "limited" dataset will be anonymized and will not contain any personal data. All 1L IO and 2L sunitinib patients are included in the "limited" dataset, but only a select number of variables necessary to fulfill the study objectives will be included.

#### 7.5. Study Size

The IMDC database has 73 patients who received 1L IO and 2L sunitinib. Power calculations were not performed as the objectives were descriptive.

#### 7.6. Data Management

CCI [REDACTED] will work with the IMDC data manager and [name] [REDACTED] to understand all available data elements from the IMDC database.

Once study site contracts have been completed, the most recent data will be transferred to CCI [REDACTED] over a secured network to ensure that the latest available data are used in the analysis. Data provided to CCI [REDACTED] will be anonymized and will not contain any personal data. After obtaining the data, CCI [REDACTED] will assess the quality of the data downloaded and work with data managers from each center to rectify any potential data entry errors and discrepancies.

#### 7.7. Data Analysis

##### Identification of study cohort

The study population of interest in this study are patients with mRCC treated with 2L sunitinib therapy following 1L IO therapy whereby the earliest date of 2L sunitinib initiation was April 15, 2014. Each patient's eligibility for this study will be verified against the eligibility criteria.

